6.4 Blinding

This is an open-label study; therefore, the subjects and Investigators will be unblinded to subject's arm. However, there will be a limited degree of blinding in the data review and data analysis process. In particular, PMI and CRO personnel will be blinded to the randomized arm as summarized in the following table:

Blinded Study Personnel	End of Blinding Period
PMI and CRO study statisticians	After the SAP finalization or PMI blind database lock ^(*) , whichever comes last.
PMI data manager	After the finalization of PMI blind database review. ^(*)
PMI safety and clinical scientists	After the finalization of PMI blind database review ^(*) . Can be actively un-blinded before that time point in case of the occurrence of any safety question, when appropriate.

(*) As part of the PMI quality control (QC) activity, data listings will be reviewed by PMI before database lock, with no access to the randomization arm information.

Any PMI and CRO personnel who are not listed in the above table will be unblinded by default.

Data and information contained in this document are considered to constitute trade secrets and confidential commercial information, and the legal protections provided to such trade secrets and confidential information are hereby claimed under the provisions of United States law. No part of this document may be publicly disclosed without the written consent of Philip Morris International.

6.5 Investigational Product Accountability and Compliance

6.5.1 Dispensing Investigational Product

During the confinement period, each mCC will be dispensed from Day -2 onwards to the subjects. Subjects in the THS 2.2 Menthol arm will be provided by the site personnel with Menthol Tobacco Sticks from Day 1 to Day 6 stick by stick. One mCC/Menthol Tobacco Stick will be allowed at a time, as per the study design, and documented in an appropriate log.

On each day of the confinement period, the time of dispense and return for each product has to be documented from Day -2 for mCC and from Day 1 for Menthol Tobacco Sticks onwards. The start of product use on each day will correspond to the time of dispense of the first mCC/Menthol Tobacco Stick. The subject must not take a puff of the Menthol Tobacco Stick during the pre-heating time. The product will not be promoted for commercial distribution or test market.

During the ambulatory period, subjects in the THS 2.2 Menthol arm will be provided THS 2.2 Menthol including anticipated amount of Menthol Tobacco Sticks to cover the period until the next study visit. An additional number of Menthol Tobacco Sticks will be dispensed to the subjects at these visits to cover for any unexpected delay to the visit schedule made by the subject. Extra delivery of THS Menthol Tobacco Sticks in between two visits may be envisaged. Subjects in the mCC arm will buy their mCCs directly from shops and will not be reimbursed.

6.5.2 Storage and Accountability

A person in the site staff designated by the Investigator will be responsible for the storage and accountability of the IPs, in accordance with the Sponsor's requirements.

The THS 2.2 Menthol and mCCs will be stored in a secured storage site with access limited to authorized personnel only. Full accountability of the distributed products will be ensured by the designated site staff.

6.5.2.1 Confinement Period

On each day of the confinement period, study site staff will record on the Accountability Log every occasion from Day -2 to time of Discharge on Day 6 that mCCs are dispensed to a subject by the study site staff and every occasion from Day 1 to time of Discharge on Day 6 that the THS 2.2 Menthol product components (i.e., THS Tobacco Stick Holder, THS Charger, THS accessories) and Menthol Tobacco Sticks are dispensed to a subject.

Subjects will return each butt of mCC immediately after use from Day -2 to Day 6 for accountability. This will be documented in the appropriate log.

Immediately after use, all tobacco plugs of all used Menthol Tobacco Sticks will be separated from the filters and the tobacco plugs will be collected from Day 1 to Day 5, using dedicated vials for accountability and subsequent analysis of potential combustion occurrences (see also Section 7.8.2.2). This will be documented in appropriate log.

6.5.2.2 Ambulatory Period

THS 2.2 Menthol Arm:

Subjects must return any unused packs, empty packs and partially used packs of Menthol Tobacco Sticks and the THS 2.2 Menthol product components they have used to the site for accountability.

All tobacco plugs from Menthol Tobacco Sticks used after check-in at the investigational site until around 11:00 PM on Day 30 Visit, Day 60 Visit, and Day 90 Visit will be collected in dedicated vials for subsequent analysis of potential combustion occurrences.

mCC Arm:

No IP accountability will be done for mCC arm.

SA Arm:

No IP accountability will be done for SA arm.

6.5.3 Investigational Product Retention

The study site will destroy or return to the Sponsor any unused Menthol Tobacco Sticks and will return to the Sponsor the THS 2.2 Menthol product components upon study completion. Retention of THS 2.2 Menthol products will be documented.

Irrespective of the study arm at the time of Discharge from the clinic, the site staff will return to the subjects any remaining mCCs given to them on the day of Admission.

6.5.4 Compliance to Investigational Product

During the confinement period, compliance for all study arms will be ensured by strict dispensation of the products (stick by stick) and collection of used Menthol Tobacco Sticks/mCC butts will be documented in the appropriate log.

During the ambulatory period, subjects in the 3 study arms will capture, Day 6 to the time of Discharge on Day 90 Visit (Day 91), the number of product used (e.g., menthol and non-menthol CC, Menthol Tobacco Sticks, or any other tobacco /nicotine-containing products including NRT) on a daily basis in the product use electronic diary. The product use electronic diary will be supplied by Sponsor and distributed to the subjects by the study site personnel. The product use electronic diary will serve as a compliance tool in the 3 arms. On Day 6, the compliance to the product will be ensured using both the accountability log (from 06:30 AM to time of discharge) and the product use electronic diary. In case of discrepancy between the log and the electronic diary entries, the electronic diary will be considered as the primary source data.

In addition, in the SA arm, compliance will be chemically verified using an exhaled CO breath test during both the confinement and at the ambulatory visits. The cut-off point for the CO breath test value to distinguish mCC use versus SA use will be 10 ppm (Benowitz et al., 2002).

6.6 Restrictions

6.6.1 Smoking Restrictions and Restrictions to the Smoking Abstinence Arm

6.6.1.1 *Confinement Period*

To avoid smoke cross-contamination among the 3 study arms, subjects in the THS 2.2 Menthol and the mCC arm must smoke in separate rooms and the subjects allocated to the SA arm should not have access to the smoking rooms. Precautions should be taken to remove cues to smoking for subjects who are randomized to the SA arm.

In the THS 2.2 Menthol and SA arms, subjects will not be allowed to smoke any mCC or use any nicotine/tobacco-containing products (including NRT) from Day 1 (06:30 AM) until the time of Discharge on Day 6. In the mCC arm, subjects will not be allowed to use the THS 2.2 Menthol, any nicotine/tobacco containing products and other mCC than brought to the site by the subject. In the SA arm, intensive support including psychological support will be provided upon the request of the subject or of the Investigator/site staff.

Smoking will generally only be allowed during the designated smoking times, from 06:30 AM onwards to around 11:00 PM (for more details on time restrictions see Section 6.2). In general, the performance of scheduled procedures has priority over the wish of a subject to use the product. However, this is different at Day 5 due to the assessment of the nicotine profile. If the subject wants to use the product at Day 5 around the time of the blood draw, he/she should use the product first and the blood will be drawn after product use.

6.6.1.2 Ambulatory Period

Subjects in the THS 2.2 Menthol arm will be instructed to exclusively use THS 2.2 Menthol and subjects in the SA arm will be instructed to remain abstinent from smoking with or without NRT.

In the THS 2.2 Menthol and mCC arms, product use will be allowed during the Day 30 Visit, Day 60 Visit, and Day 90 Visit (for more details on time restrictions see Section 6.2).

Subjects in the SA arm may use NRT (no other medication supportive to smoking abstinence will be allowed) if considered necessary by the Investigator or if requested by the subject. NRT products will be used as per the product label, and may be purchased by subjects at a pharmacy. Subjects will be reimbursed. Intensive support including psychological support will be provided upon the request of the subject or of the Investigator/site staff.

6.6.2 Dietary Restrictions

6.6.2.1 Confinement Period

A standard diet will be designed by a dietitian. For each meal, the caloric and fat content should be controlled in order to avoid a “high-fat” diet. The FDA guidance on food-effect studies for bioequivalency testing identifies a high-fat diet as a diet which maintains “approximately 50 percent of total caloric content of the meal and is high in calories (approximately 800 to 1000 calories) (FDA, 2002).”

In order to avoid any effect on assessment of BoExp, grilled or pan-fried meat, smoked pre-cooked meats (e.g., tuna, ham, corned beef, and meats), smoked bacon and sausage will not be permitted (Tiffany et al., 1991). In addition, to avoid any effect on the measurement of CYP1A2 activity, alcohol, broccoli, Brussels sprouts, cauliflower, grapefruit, and xanthine-containing foods and beverages (coffee, tea, chocolate, cocoa, mate, guarana, etc.) will be forbidden (Faber et al., 2004) except when the subject is asked to take caffeine tablet for CYP1A2 measurement. Consumption of quinine-containing drinks (e.g., tonic water) will not be allowed.

Subjects are not allowed to bring their own food or beverages to the investigational site. Meals will be served according to the schedules provided in Section 9. Additional light snack, fruits, and raw vegetables can be distributed to the subjects without restrictions at any time during confinement as long as they fulfill the above requirements. Consumption of water is allowed as desired. The same menu and meal schedule will be administered uniformly for all subjects in all study arms. In addition for the purpose of the Ames test planned on Day 0 and Day 5, the menus served on Day -1 and Day 4 will be identical.

Fasting state has to be observed for at least 10 hours prior to blood draws for:

Data and information contained in this document are considered to constitute trade secrets and confidential commercial information, and the legal protections provided to such trade secrets and confidential information are hereby claimed under the provisions of United States law. No part of this document may be publicly disclosed without the written consent of Philip Morris International.

1. Safety laboratory on screening, Day 0, Day 6.
2. Risk markers in serum/plasma/blood on Day 0 and Day 6.
3. Serum/plasma bio-banking samples for further analysis of BoExp and risk markers on Day 0, and Day 6.
4. Blood bio-banking for transcriptomics on Day 0 and Day 6.
5. Oxysterols in plasma on Day 0 and Day 6.

On Day 0 and Day 6, subjects must not have eaten at least 30 minutes prior to collection of buccal and nasal epithelial samples.

6.6.2.2 Ambulatory Period

The above dietary restrictions are not applicable for the ambulatory period. However, 1 day prior to the Day 90 Visit, and during the visit on site, subjects will be asked by the site staff to refrain from consuming grapefruit or grapefruit-containing products, or quinine-containing drinks (e.g., tonic water). Alcohol, broccoli, Brussels sprouts, cauliflower, chargrilled meat, xanthine-containing foods and beverages (e.g., coffee, tea, chocolate, cocoa, mate, guarana) will not be allowed on site during the Day 90 Visit.

A fasting state has to be observed for at least 10 hours prior to blood draws for:

1. Safety laboratory on Day 30 Visit (Day 31), Day 60 Visit (Day 61), and Day 90 Visit (Day 91).
2. Risk factor assessments in serum/plasma/blood on Day 30 Visit (Day 31), Day 60 Visit (Day 61), and Day 90 Visit (Day 91).
3. Serum/plasma bio-banking samples for further analysis of BoExp and risk markers at the Screening Visit, on Day 90 Visit (Day 91).
4. Blood bio-banking for transcriptomics on Day 90 Visit (Day 91).
5. Oxysterols in plasma on Day 90 Visit (Day 91).

On Day 90 Visit (Day 90), subjects must not have eaten at least 30 minutes prior to collection of nasal epithelial and buccal samples.

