7.5.2.2 CYP1A2 activity test

CYP1A2 activity will be assessed in plasma by measuring PX and CAF concentrations and calculating the PX/CAF molar metabolic ratio (Faber et al., 2004) on Day 0, Day 5, and Day 90 Visit (Day 90). Samples to measure PX and CAF will be drawn approximately 6 hours (± 15 minutes) after the intake of one “vivarin” caffeine tablet (around 200 mg caffeine) with 240 mL ± 10 mL water (Faber et al., 2004).

The exact time of intake of the caffeine tablet in the morning and of the time of blood sampling 6 hours [± 15 minutes] later must be recorded.

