Prior to check-out of the given visit		Information on the risk of smoking/smoking cessation advice and debriefing	
Check-out		End of the Visit	

Abbreviations: 11-DTX-B2 = 11-dehydro-thromboxane B2; AE = adverse event; BoExp = biomarkers of exposure; CO = carbon monoxide; COHb = carboxyhemoglobin; HDL: high density lipoprotein; hs CRP: high sensitivity lipoprotein; HST = human smoking topography; LDL: low density lipoprotein; mCC = menthol conventional cigarette(s); MCEQ = Modified Cigarette Evaluation Questionnaire; MNWS = Minnesota Nicotine Withdrawal Scale; SAE = serious adverse event; s-ICAM-1: soluble inter-cellular Molecule 1; TC: total cholesterol; TG = triglycerides; THS = tobacco heating system; QSU = Questionnaire of Smoking Urges; WBC = white blood cell count.

The procedures for the last visit which will be conducted on Day 90 Visit +/- 5 days of the study are shown in Table 18.

The time of opening and end of the visit are given as an estimate.

Table 18. Time Schedule – Day 90 Visit (from the time of check-in in the morning prior to 08:30 AM of Day 90 to time of discharge of Day 91)

Time	Blood sample	Procedures	Additional information
Start of procedure		Day 90	
In the morning		Opening of the Visit	No product restriction prior to the opening of the visit. Product use will be allowed on site in the THS 2.2 Menthol and mCC arms from the time of check-in in the morning to around 11:00 PM The use of THS 2.2 menthol in smokers allocated to mCC and SA arms will be forbidden
		AE/SAE questioning; Concomitant medication	At any time during the day
		Support for smoking abstinence (SA arm only), if needed	At any time of the day
08:30 AM-09:30 AM		Start of HST recording for 4-hour	In the THS 2.2 Menthol and mCC arms, the HST SODIM® device has to be used for all smoking events if compatible mCCs are smoked HST recording will be done only on the subject's assigned product
09:00 ± 30 min		Start of collection of 24-hour urine fraction	The subject must empty his bladder and discard the urine prior to starting urine collection
Before 11:00AM		Breakfast with a caffeine tablet containing approximately 200 mg of caffeine ± 240 mL ±10 mL of water	The time of caffeine tablet intake must be recorded
10:00 AM-12:30 PM		CO breath test	Irrespective of the time of product use
10:00 AM-12:30 PM	√	COHb in blood	Irrespective of the time of product use

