#### 12.6.2.4 CYP1A2 Activity

CYP1A2 activity will be measured in plasma on Day 0, Day 5 and Day 90. In this study the CYP1A2 activity will be calculated using the molar ratio of PX and CAF, as described in Section 7.1.3 “CYP1A2”. Descriptive statistics of the values and percent change on Days 5 and 90 from Day 0 and supportive listings will be provided.

The analysis will compare the log-transformed Day 5 values between the THS 2.2 Menthol and mCC arms and between the THS 2.2 Menthol and SA arms. ANCOVA models will be used on CYP1A2 activity levels with terms for log-transformed baseline, sex, average daily mCC consumption over the last 4 weeks as reported during screening and randomization arm. No adjustment will be made for multiple comparisons. If the results from the Day 5 analysis are significant (one-sided p-value <0.025) then the statistical significance will be repeated for the analysis at the Day 90 values. The SAS code will be similar to that described in Section 12.6.1.3 “Sensitivity Analysis”.

Geometric LS means for each product along with the ratio (THS 2.2 Menthol :mCC) and 95% CI will be presented in the tables.

CYP1A2 activity will also be examined to compare the observed reductions in THS 2.2 Menthol vs. SA using the same methodology as above.

If there are any CYP1A2 assessments performed within 5 half-lives since the use of a concomitant medication affecting CYP1A2 activity, the analysis will be repeated by excluding these assessments for both the PP Set and FAS

All summaries and analyses will be performed on the FAS and PP Set.

The data will be presented in the below outputs:

TFL number	Title
TABLES	
15.2.4.23.1	Descriptive Statistics of CYP1A2 Activity (%) – PP Set
15.2.4.23.1.1	Descriptive Statistics of CYP1A2 Activity (%) Excluding Assessments within 5 Half-Lives of a Concomitant Medication Affecting CYP1A2 Activity – PP Set
15.2.4.23.2	Descriptive Statistics of CYP1A2 Activity (%) – FAS
15.2.4.23.2.1	Descriptive Statistics of CYP1A2 Activity (%) Excluding Assessments within 5 Half-Lives of a Concomitant Medication Affecting CYP1A2 Activity – FAS
15.2.4.24.1	Analysis of CYP1A2 Activity (%) – PP Set
15.2.4.24.1.1	Analysis of CYP1A2 Activity (%) Excluding Assessments within 5 Half-Lives of a Concomitant Medication Affecting CYP1A2 Activity – PP Set
15.2.4.24.2	Analysis of CYP1A2 Activity (%) – FAS

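### The xanthine rule before the Day 90 CYP1A2 test is looser than before the Day 0 and Day 5 tests, so permitted dietary caffeine can make the Day 90 PX/CAF ratio non-comparable

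*Protocol*

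**What the plan says.** Protocol 6.6.2.1 (confinement) gives its reason for the diet rule: "to avoid any effect on the measurement of CYP1A2 activity, alcohol, broccoli, Brussels sprouts, cauliflower, grapefruit, and xanthine-containing foods and beverages" are forbidden, apart from the test tablet itself. Confinement runs from Day -2 to Day 6, so the rule covers the Day 0 and Day 5 tests.

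Protocol 6.6.2.2 then states: "The above dietary restrictions are not applicable for the ambulatory period". From one day before the Day 90 Visit, "subjects will be asked by the site staff to refrain from consuming grapefruit or grapefruit-containing products, or quinine-containing drinks". Xanthines are not in that sentence. They appear only in the next one: "xanthine-containing foods and beverages (e.g., coffee, tea, chocolate, cocoa, mate, guarana) will not be allowed on site during the Day 90 Visit". The Explanation of Terms starts the visit at check-in on the morning of Day 90, before 08:30.

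On the test itself, Protocol 7.5.2.2 says: "Samples to measure PX and CAF will be drawn approximately 6 hours" after the tablet. Protocol 9.3, Table 18 schedules the Day 90 tablet before 11:00: "Breakfast with a caffeine tablet containing approximately 200 mg of caffeine".

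SAP 12.6.2.4 summarises Day 5 and Day 90 values and their percent change from Day 0. It fits ANCOVA on the log scale with log baseline as covariate. For Day 90 it adds: "If the results from the Day 5 analysis are significant (one-sided p-value <0.025) then the statistical significance will be repeated". The only interference it handles is medication affecting CYP1A2, through a repeat analysis without those assessments.

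**The concern.** The PX/CAF ratio indexes CYP1A2 activity only if the caffeine and paraxanthine in the sample come mainly from the tablet. Caffeine drunk earlier has had longer to become paraxanthine, so any residue pushes the ratio up. The plan controls this at the first two tests and leaves it open at the third. Grapefruit and quinine are restricted from the day before the visit, but the probe substance is not.

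At stake is one secondary endpoint, the change in CYP1A2 activity on Day 5 and Day 90. If Day 90 values carry dietary caffeine and Day 0 and Day 5 values do not, the Day 90 percent change mixes enzyme activity with coffee habits. Variable intake also widens the spread of Day 90 values.

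**Working it through.** **1. Xanthine-free time guaranteed before each tablet**

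- Day 0: admission procedures run until 18:30 on Day -2 (Protocol Table 8) and the earliest tablet is at 10:00 on Day 0 (Table 10). 5.5 + 24 + 10 = 39.5 h at least.
- Day 5: from 18:30 on Day -2 to 10:00 on Day 5 (Table 15). 5.5 + 6 × 24 + 10 = 159.5 h, about 6.6 days of restricted diet. The Day 0 test tablet is the only caffeine in between, at least 118.5 h earlier (11:30 on Day 0 to 10:00 on Day 5).
- Day 90: only the time from check-in (before 08:30) to the tablet (before 11:00). Check-in at 08:30 and a tablet at 11:00 give 2.5 h. No minimum is stated.

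**2. Could another rule close the gap?** The 10-hour fasts in 6.6.2.2 precede blood draws on Days 31, 61 and 91, so none precedes the Day 90 tablet. No pre-tablet caffeine or paraxanthine sample is described, and no record of dietary caffeine.

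**3. Illustrative size.** The plan has no figure to reproduce, and none of the following inputs is in the documents: one-compartment kinetics, immediate absorption, 80% of caffeine converted to PX, caffeine half-life 3-7 h, PX half-life 3-5 h, coffees of 100 mg. The tablet (200 mg) is set at 10:00 and the sample at 16:00.

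For dose D taken t hours before sampling, with kc = ln 2 / (caffeine half-life) and kp = ln 2 / (PX half-life):

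- CAF = D·exp(−kc·t)
- PX = 0.8·D·kc/(kp − kc)·[exp(−kc·t) − exp(−kp·t)]; when kp = kc, the limit 0.8·D·kc·t·exp(−kc·t)

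Doses are summed and PX/CAF is compared with the tablet alone. The conversion fraction and the molar factors cancel in this relative change.

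Worked case (caffeine 5 h, PX 4 h, so kc/(kp − kc) = 4):

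- Tablet alone, t = 6: CAF 87.06, PX 52.30, ratio 0.601.
- Add one coffee at 07:30 on Day 90, t = 8.5: CAF 30.78, PX 25.13. Ratio 77.43/117.83 = 0.657, or +9.4%.
- Add three coffees on Day 89 as well (08:00, 13:00, 20:00): ratio 94.58/127.64 = 0.741, or +23.3%.

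| Half-lives, caffeine / PX (h) | One coffee 07:30 | Three on Day 89 plus 07:30 |
|---|---|---|
| 3 / 3.1 | +9% | +15% |
| 4 / 4 | +10% | +22% |
| 5 / 4 | +9% | +23% |
| 5 / 5 | +11% | +32% |
| 6 / 5 | +10% | +33% |
| 7 / 5 | +10% | +35% |

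A single coffee at 20:00 on Day 89, with nothing on Day 90, gives +5% to +18%, so the on-site ban alone does not remove the effect. Three coffees finished by 18:30 on Day -2 raise the Day 0 ratio by only about 0-6%, so the confinement rule largely works.

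**4. Between arms.** Same four coffees, changing only the caffeine half-life (4 h in mCC, 6 h in THS) and keeping the PX half-life equal in both arms:

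| PX half-life (h) | THS:mCC, tablet only | With four coffees |
|---|---|---|
| 3 | 0.569 | 0.575 |
| 4 | 0.563 | 0.573 |
| 5 | 0.560 | 0.573 |

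The ratio moves by about 1-2%. With the 07:30 coffee alone it moves slightly the other way (PX 4 h: 0.563 to 0.556).

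**The case against.** The planned inference is largely insulated. SAP 12.6.2.4 compares THS with mCC and THS with SA within the same day, and all arms follow the same Day 90 diet rule. A carry-over factor common to the arms cancels in those ratios. Day 90 significance is looked at only after a significant Day 5 result, and Day 5 is well protected. The protocol objective is to describe the change, and the endpoint is secondary. All of this stands.

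A reader might go further and infer that carry-over biases the Day 90 comparison: CYP1A2 activity is expected to fall on abstinence or switching, slower clearance leaves more residue, so THS and SA would be inflated more than mCC. The documents do not support this. Step 4 gives a shift of 1-2%, with its sign depending on when the coffee was drunk. A larger shift appears only if the paraxanthine half-life is also lengthened in the THS arm, for which the plan gives no basis. Intake could differ by arm, but nothing in the documents says so.

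A reader might also take carry-over as a fact. The plan only permits it and cannot detect it.

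Cancellation between arms does not, however, repair the percent change from Day 0 or remove the noise from varying intake.

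**Conclusion.** The concern holds as an inconsistency between Protocol 6.6.2.1 and 6.6.2.2 for the same test. Day 0 and Day 5 have at least about 39.5 h and 6.6 days under a xanthine ban. Day 90 has only the hours since check-in, with no means of detecting earlier intake.

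Under the assumptions in step 3, permitted intake raises Day 90 PX/CAF by roughly 10% (one morning coffee) to 35% (four coffees, slow elimination). With no true change in activity, a subject would then show a rise of that size from Day 0. The range rests entirely on assumed half-lives, conversion and intake. The inconsistency itself rests on the text alone.

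The consequence is added noise, and a Day 90 value and percent change that are not comparable with Day 5. Bias between arms is not established, and the primary endpoints are untouched. This is a cheap improvement to a secondary endpoint and does not threaten the study's conclusions.

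**What to change.** - **Protocol 6.6.2.2:** reconcile with 6.6.2.1 by adding xanthine-containing foods and beverages to the existing sentence that applies from one day before the Day 90 Visit. The other foods barred only on site need not be added on this argument: caffeine is the probe, and no comparable case has been made for them.
- **Check-in on Day 90:** record any caffeine intake in that period, with time and approximate amount.
- **SAP 12.6.2.4:** beside the existing medication exclusion, add a supportive repeat of the Day 90 analysis without subjects who report intake. Keep the planned analysis as the main one, because this exclusion is made after randomization.

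Cost: one sentence in the protocol and subject instructions, one question at check-in and one further table. Subjects, who already follow a restriction that day, go without caffeine for a day. The supportive analysis may be small: Protocol 12.2 (Table 22) expects only about 40 THS subjects in the Day 90 per-protocol set, and fewer would remain if many report caffeine. If Day 90 visits have already taken place, the study report should state that the Day 90 percent change was measured under a different xanthine rule.
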